The MYK-461 starting dose will be 10 mg for subjects who weigh \leq 60 kg and 15 mg for subjects who weigh $>$ 60 kg. At the end of Week 4 (Day 28), each subject's LVEF will be evaluated, and the subject's dose may be increased, decreased, or remain unchanged based on the predetermined criteria in Table 1, in consultation between the investigator and the medical monitor. If MYK-461 plasma concentration exceeds 750 ng/mL at Week 2, no dose increase is allowed, regardless of LVEF data at Week 4; however, dose decrease per LVEF data is allowed in this circumstance. The subject will subsequently receive that dose from Week 5 through Week 12.

Table 1 Part A Week 4 Dose Adjustment Criteria

Percent Decrease From Baseline in LVEF at the End of Week 4 (Day 28)	Action for MYK-461 Dose Week 5-Week 12 ^a
< 10	increase dose by 10 mg
\geq 10 and < 15	increase dose by 5 mg
\geq 15 and < 20	no change in dose
\geq 20	decrease dose by 5 mg

LVEF, left ventricular ejection fraction

^b No dose increase allowed if plasma concentration of MYK-461 $>$ 750 ng/mL at Week 2.

Part B:

The MYK-461 starting dose will be 2 mg. At the end of Week 4 (Day 28), each subject's resting (non-provoked) peak instantaneous LVOT gradient and LVEF from the Week 4 TTE will be evaluated. The subject's dose will be increased to 5 mg or remain unchanged based on the predetermined criteria in [Table 2](#) below, in consultation between the investigator and the medical monitor. If MYK-461 plasma concentration exceeds 300 ng/mL at Week 2, no dose increase is allowed. The subject will subsequently receive that dose from Week 5 (Day 29) through Week 12.

Table 2 Part B Week 4 Dose Adjustment Criteria

Percent Decrease From Day 1 in Resting TTE Instantaneous Peak LVOT gradient at the End of Week 4 (Day 28)	Action for MYK-461 Dose Week 5-Week 12 ^a
< 50%	increase dose to 5 mg
≥ 50%	no change in dose

; LVOT, left ventricular outflow tract;

^a No dose increase allowed if plasma concentration of MYK-461 > 300 ng/mL at Week 2.

For all subjects who provide consent, blood will be drawn prior to dosing on Day 1 for assessment of HCM genotype and potentially additional deoxyribonucleic acid (DNA) sequencing.

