7.3 Dose Adjustment

All subjects in Part A will be assigned to a starting dose of oral MYK-461 based on body weight for doses ≥ 10 mg, which they will receive QD for 4 weeks. Subjects in Part B will be assigned a starting dose of 2 mg. At the Week 4 visit, dose adjustment may be performed based on the predetermined criteria in [Section 4, Table 1 \(Part A\) and Table 2 \(Part B\)](#). The subject will subsequently receive that dose from Week 5 (Day 29) through Week 12.

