9.1 **Efficacy and Pharmacodynamic Assessments**

9.1.1 *Echocardiography and Cardiopulmonary Exercise Testing*

Details are provided in the Study Reference Manual. Echocardiography and CPET should be performed prior to dosing. All echocardiography data will be sent to a central imaging laboratory. CPET data will also be sent to a central laboratory.

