- Retrieve previous cardiac monitoring skin patch and apply a new one
- Optical biosensor pulse wave analysis (consenting subjects)

Open-label administration of MYK-461 at site.

Complete the following procedures postdose (when indicated, timing of assessments is approximate):

- Resting vital signs at 1 hour postdose
- 12-lead ECG (triplicate) at 1 hour postdose
- AE assessment

9.5.3 Day 4

- Contact subject via telephone to determine the subject's status and ascertain whether the subject is experiencing any AEs. Information on concomitant medications should also be collected.

9.5.4 Weeks 1, 2, 3, 4, 5, 6, 7, and 8

Complete the following procedures before administering the oral dose of study medication.

- Abbreviated cardiopulmonary physical examination, with other systems assessed as directed by interval history
- 12-lead ECG (triplicate)
- Vital signs after resting for at least 5 minutes
- Resting TTE
- Hemodynamic stress echocardiography (Week 4 only) after 4 hour fast
- Blood samples for
 - hematology, serum chemistry (Weeks 4 and 8 only)
 - NT-proBNP (Weeks 4 and 8 only)
 - PK, within ≤ 2 hours prior to dosing
- Pregnancy test (blood or urine) for women of childbearing potential, based on standard at institution (Weeks 4 and 8 only)
- Retrieve previously applied cardiac monitoring skin patch (Weeks 2, 4, 6, and 8 only) and apply a new patch. At Week 8 only, the subject should be provided with an additional patch to be applied at Week 10.
- Optical biosensor pulse wave analysis (consenting subjects) (Weeks 1, 2, 4, and 8 only)
- Concomitant therapy assessment
- AE assessment
- Dyspnea NRS
- Study medication compliance
- Potential dose adjustment (Week 4 only)
- Open-label MYK-461 administration at site

9.5.5 Week 10

- Contact subject via telephone to determine the subject's status and ascertain whether the subject is experiencing any AEs. Information on concomitant medications should also be collected.

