9.5.6 Week 12/Early Termination

- Complete physical examination; includes neurological examination and weight
- 12-lead ECG (triplicate)
- Vital signs after resting for at least 5 minutes
- Resting TTE
- Hemodynamic stress echocardiography after 4 hour fast
- CPET after a 4-hour fast (water is allowed). CPET may be conducted at the Week 12 visit or anytime between Weeks 10 and 12. If CPET and hemodynamic stress echocardiography are conducted at the same visit, the hemodynamic stress echocardiography should be conducted first, followed by the CPET.
- Blood samples for
 - Hematology and serum chemistry
 - NT-proBNP
 - Potential exploratory biomarker analysis
 - PK (within ≤ 2 hours prior to dosing)
- Pregnancy test (blood or urine) for women of childbearing potential, based on standard at institution
- Urine sample for urinalysis
- Retrieve previously applied cardiac monitoring skin patch and apply a new patch. The skin patch is only required for up to 2 weeks of wear time.
- Optical biosensor pulse wave analysis (consenting subjects)
- Concomitant therapy assessment
- AE assessment
- Study medication compliance
- Dyspnea NRS
- KCCQ
- NYHA class
- Open-label MYK-461 administration at site

9.5.7 ***Week 16/End of Study***

- Complete physical examination; includes neurological examination and weight
- 12-lead ECG (triplicate)
- Vital signs after resting for at least 5 minutes
- Resting TTE
- Hemodynamic stress echocardiography after 4 hour fast
- Blood samples for
 - Hematology and serum chemistry
 - NT-proBNP
 - PK
- Urine sample for urinalysis
- Pregnancy test (blood or urine) for women of childbearing potential, based on standard at institution
- Retrieve cardiac monitoring skin patch
- Optical biosensor pulse wave analysis (consenting subjects)
- Concomitant therapy assessment
- AE assessment
- Dyspnea NRS
- KCCQ
- NYHA class

9.5.8 ***Unscheduled Visits***

At the investigator's discretion, unscheduled visits may be conducted for the assessment of AEs, physical examinations, vital signs, laboratory tests, ECGs, and/or TTEs. All information collected from unscheduled visits will be recorded on the eCRF and included in the clinical database.

9.6 **Visit Window and Missed Visits**

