10 EVALUATION, RECORDING, AND REPORTING OF ADVERSE EVENTS

10.1 Definitions

10.1.1 Adverse Event

An AE is any untoward medical occurrence, or the deterioration of a preexisting medical condition (other than the condition that is being treated by the study) associated with the use of a study medication in humans, whether or not it is considered related to the study medication. An AE (also referred to as an adverse experience) can therefore be any unfavorable and unintended sign (e.g., tachycardia, enlarged liver, clinically important abnormal laboratory result or diagnostic procedure), subject-reported symptom (e.g., nausea, chest pain), or evidence of any disease activity temporally associated with the use of a study medication, whether or not related to the study medication.

In clinical studies, an AE can include an undesirable medical condition occurring at any time after the subject has signed informed consent, including run-in or washout periods, even if no specific treatment has been administered.

Preexisting medical conditions (other than natural progression of the disease being studied) judged by the investigator or subject to have worsened in severity or frequency or changed in character during the protocol-specified AE reporting period will be reported as AEs or SAEs as appropriate.

Imaging-based assessments of decrease in contractility are not considered AEs unless associated with symptoms or signs of clinical concern on the part of the investigator. Such events should be categorized as an AE defined in terms of those symptoms or signs.

An AE or SAE can also be a complication that occurs as a result of protocol-mandated procedures (e.g., invasive procedures such as biopsies).

For MyoKardia to collect additional information about clinically important laboratory results or diagnostic tests (e.g., blood, ECG, imaging), at a minimum, the following abnormalities should be captured on the AE eCRF:

- Any test result that meets the definition of an SAE
- Any clinically important test abnormality that suggests a disease and/or organ toxicity that has worsened or is new (e.g., $>3\times$ deviation from the upper or lower limit of the analyzing laboratory reference range, or as otherwise specified in the protocol)
- Any test abnormality that required the subject to have study medication discontinued or interrupted or in the clinical judgment of the investigator.

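### Part A's one LVEF dosing rule acts only at Week 4, and its lowest row continues MYK-461 at 5 mg less however low LVEF is; no LVEF level for withholding is stated

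*Protocol*

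**What the plan says.** Protocol section 4 (repeated in the Synopsis and in SAP 3.1) bases the Part A dose for Weeks 5 to 12 on Table 1, headed "Percent Decrease From Baseline in LVEF at the End of Week 4 (Day 28". It has four rows:

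- fall below 10%: add 10 mg
- fall of 10% to under 15%: add 5 mg
- fall of 15% to under 20%: keep the dose
- fall of 20% or more: take off 5 mg

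Section 7.3 adds only a pointer: "At the Week 4 visit, dose adjustment may be performed based on the predetermined criteria". The visit list in 9.5.4 confirms the timing: "Potential dose adjustment (Week 4 only". One further limit bears on increases: "If MYK-461 plasma concentration exceeds 750 ng/mL at Week 2, no dose increase is allowed".

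Resting TTE is done at Weeks 1 to 8, 12 and 16, and 9.1.1 says "Echocardiography and CPET should be performed prior to dosing". LVEF is therefore measured before the visit dose at every on-treatment site visit.

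On recording, 10.1.1 says "Imaging-based assessments of decrease in contractility are not considered AEs unless associated with symptoms or signs of clinical concern". It also asks for AE capture of "Any test abnormality that required the subject to have study medication discontinued or interrupted".

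In Part B, section 4 says LVEF will be looked at in Week 4, but Table 2 uses only the resting gradient.

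**The concern.** Reduced contractility is the effect to watch with this drug. Sections 1.3 and 8.1 say that dose-limiting toxicity in animals came from exaggerated pharmacology, and the 25 mg cohort of the healthy-subject multiple-dose study was stopped because of LVEF falls. Section 7.4 gives numeric withholding limits and a rechallenge procedure for liver tests. No comparable limit is stated for LVEF.

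Two things follow from Table 1 as written. A subject with a very low Week 4 LVEF gets the same action, continued dosing at 5 mg less, as one who has just reached a 20% fall. At every other visit the TTE is tied to no stated dosing action. Whether a subject with a low reading is held then depends on individual judgement, which may differ between about seven sites.

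**Working it through.** The plan gives no figure for this point, so there is nothing to reproduce. The check has three steps.

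**1. What LVEF each row of Table 1 permits**

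Inputs: entry LVEF of at least 55% (inclusion 6); LVEF below 45% labelled LV systolic dysfunction (exclusion 9). Table 1 is read as relative change, which matches how 1.3 and 8.1 describe the 20% criterion in the earlier studies. LVEF after a relative fall x from baseline B is B × (1 − x). The fall that reaches 45% is 1 − 45/B.

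| Baseline | 20% fall | 30% fall | 40% fall | Fall that reaches 45% |
|---|---|---|---|---|
| 55% | 44.0% | 38.5% | 33.0% | 18.2% |
| 60% | 48.0% | 42.0% | 36.0% | 25.0% |
| 65% | 52.0% | 45.5% | 39.0% | 30.8% |
| 70% | 56.0% | 49.0% | 42.0% | 35.7% |
| 75% | 60.0% | 52.5% | 45.0% | 40.0% |

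Every LVEF in the three middle columns falls in the row that continues dosing at 5 mg less.

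The keep-the-dose row ends just short of a 20% fall. It reaches below 45% only if 0.80 × B < 45, that is, if B < 56.25%. From 55% it covers LVEF from just under 45% (fall of 18.2%) to just above 44% (fall just under 20%).

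**2. Whether a 5 mg cut acts like a hold**

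Inputs: half-life of about 8 days (1.2.1). Linear, first-order accumulation is assumed. With first dose d1, dose d2 from Day 28 and half-life h, the level on day t in mg-equivalents is

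d1 × (1 − 2^(−t/h)) + (d2 − d1) × (1 − 2^(−(t−28)/h)).

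At h = 8, the Week 4 level is 13.67 on 15 mg and 9.12 on 10 mg. The later levels, as a share of Week 4, are:

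| Action at Week 4 | Week 5 | Week 6 | Week 12 | Week 5, h = 6 to 12 days |
|---|---|---|---|---|
| 15 to 10 mg | 12.00/13.67 = 88% | 11.09/13.67 = 81% | 10.03/13.67 = 73% | 83–94% |
| 10 to 5 mg | 7.24/9.12 = 79% | 6.22/9.12 = 68% | 5.03/9.12 = 55% | 73–88% |
| Withhold (from 15 mg) | 7.46/13.67 = 55% | 4.07/13.67 = 30% | – | 45–67% |

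The shares for withholding are the same from 10 mg. The stated action lowers exposure much more slowly than a hold. These figures describe exposure, not LVEF.

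After the largest increase, 15 to 25 mg, the level is 24.00 at Week 8 and 24.91 at Week 12, a ratio of 96% (92–98% for h of 12 to 6 days). The TTEs at Weeks 5 to 8 therefore cover nearly all of the rise, although none is scheduled between Weeks 8 and 12. The main gap is a rule that acts on the TTEs, not the TTE schedule.

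**3. Whether another provision supplies the level**

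- 5.5.1: the investigator or sponsor may withdraw a subject for an AE, noncompliance, study termination or other reasons. No LVEF level.
- 7.5: advises a β-agonist and supportive care. It is triggered by AEs potentially related to reduced cardiac output and does not mention withholding.
- 10.1.1: a fall seen only on imaging is not an AE without symptoms or signs of clinical concern, so an asymptomatic fall would not ordinarily reach 7.5. The capture of test abnormalities that led to interruption records a stop but does not say when to stop.
- 4.2: the IDMC reviews data and advises. No threshold is given.
- 13.2.7: a deviation is allowed to remove an immediate hazard. No threshold.
- 9.3.4: refers to alert values in 7.3, but for vital signs, and 7.3 lists none.

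**The case against.** The strongest reply is that the protocol does not force anyone to keep dosing. Table 1 is permissive and is applied in consultation with the medical monitor. Section 5.5.1 makes withdrawal a protocol provision, 13.2.7 allows an immediate departure for a hazard, and the IDMC reviews data regularly. With TTE at Weeks 1 to 8 and 12, a large fall would probably be seen. All of this stands. A reader might infer from Table 1 that stopping is barred, or that low LVEF would go unnoticed; the documents support neither.

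The baseline also matters. Section 1.1 says that ejection fraction in HCM is often supranormal. From 75%, even a 40% fall only reaches 45%. The larger falls in the table above are illustrations with no documented frequency.

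Increases are constrained too. None is allowed above 750 ng/mL at Week 2, and 25 mg is reachable only from 15 mg after a fall below 10%. One might be tempted to carry over the 25 mg healthy-subject result (5 of 12 blinded subjects in 1.2.3 and 1.3; 3 of 10 treated in 8.1). It shows that the effect is real, in asymptomatic subjects, but it does not estimate a rate in Part A patients selected for a small fall at the starting dose.

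The half-life comes from single doses of a suspension in healthy men. Echocardiography details are delegated to the Study Reference Manual, which was not available and may hold a limit. Section 2.2 speaks of Part A exposures as already achieved, so Part A dosing may be over, although the documents do not establish that.

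None of this supplies an LVEF trigger. Discretion permits a hold but does not say when one is due.

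**Conclusion.** The point holds as a missing prespecified safety trigger. Part A has one LVEF dosing rule, used once, with an open-ended lowest row that continues the drug. From a baseline of 55%, that row covers LVEF of 44% and 33% alike, and the row above leaves the dose unchanged at LVEF between 44% and 45%. Below a baseline of 56.25%, therefore, the table can keep the dose at an LVEF that exclusion 9 labels systolic dysfunction. The concern shrinks as baseline rises.

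A reader might go further and conclude that the trial ran without any LVEF limit, or that many subjects would fall below 45%. The documents do not show either: the manual is unseen, some pages were removed, and no rate is given.

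The LVEF figures rest on the relative reading of Table 1. The exposure figures rest on linear kinetics and a half-life of 6 to 12 days. The absence of a trigger rests on neither.

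**What to change.** Add to section 7.3, in substance:

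*Parts A and B: if any on-treatment resting TTE shows LVEF below 45% by the site reading, MYK-461 is withheld and the medical monitor is consulted. Dosing may resume only after LVEF has recovered to [level], at [lower dose]. This overrides Tables 1 and 2.*

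The 45% comes from exclusion 9. It is a history criterion, not an on-treatment safety limit, so the sponsor and IDMC may set another number. They should also fill in the recovery level and the restart dose. A subject on 2 mg has no lower supplied strength, so the text must say whether that subject restarts at 2 mg or stops. Because an absolute limit would not catch a fall from 75% to 45%, they may wish to add a relative one.

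Part B belongs in the rule because LVEF is looked at there in Week 4 with no criterion attached, β-blockers are allowed, and Part A may already be complete. If the Study Reference Manual holds a limit, state it in 7.3. Writing *relative* into the Table 1 heading would remove an ambiguity.

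**Cost.** A protocol amendment with IDMC and ethics committee review. TTEs already precede dosing, but the site must read LVEF before giving the visit dose. Follow-up TTEs fit 9.5.8, under which "unscheduled visits may be conducted for the assessment of AEs, physical examinations, vital signs, laboratory tests, ECGs, and/or TTEs". With about 10 subjects per part, each subject still withheld at Week 12 removes about 1/10 = 10% of that part's on-treatment Week 12 data; a hold that ends earlier costs less.

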4.1 Study Duration

The expected study duration is approximately 8 months (4 months for recruitment and 4 months for study conduct) for Part A and approximately 10 months for Part B (18 months in total). Each subject is expected to be in the study no more than 140 days: up to 28 days for screening and up to 112 days for study conduct.

4.2 Independent Data Monitoring Committee

An Independent Data Monitoring Committee (IDMC) will regularly review study data. The role of the IDMC will be to help identify and manage any emerging safety issues, advise the investigators and Sponsor on any important emerging study conduct issues, and serve in an advisory role concerning the evaluation procedures and methodologies being employed to survey and detect potential safety signals.

5 SELECTION AND WITHDRAWAL OF STUDY POPULATION

5.1 General Study Population and Clinical Sites

Approximately 20 subjects with symptomatic HCM and LVOT obstruction are expected to enroll in this study at 7 clinical sites in the United States (US).

5.2 Inclusion Criteria

Each subject must meet the following criteria to be enrolled in this study.

1. Able to understand and comply with the study procedures, understand the risks involved in the study, and provide written informed consent according to federal, local, and institutional guidelines before the first study-specific procedure.
2. Men or women 18 to 70 years of age at the Screening visit.
3. Diagnosed with HCM (hypertrophied and non-dilated left ventricle in absence of systemic or other known cause), with LV wall thickness ≥ 15 mm at time of initial diagnosis or ≥ 13 mm with a positive family history of HCM.
4. Body mass index (BMI) 18 to 37 kg/m², inclusive, at the Screening visit, calculated using the institution's standard formula.
5. All safety laboratory parameters (chemistry, hematology, and urinalysis) within normal limits (laboratory reference range) at the Screening visit as assessed by the central laboratory, or if outside of the limits must meet both of the following criteria:
 - considered by the investigator to be clinically unimportant
 - if a liver function test result, must be $< 1.5 \times$ the upper limit of the laboratory reference range.
6. Has documented LVEF $\geq 55\%$ at the Screening visit as determined by the investigator and the investigational site's echocardiography laboratory.
7. Resting LVOT gradient ≥ 30 mmHg and post-exercise peak LVOT gradient ≥ 50 mm Hg at the Screening visit as determined by the investigator and the investigational site's echocardiography laboratory.
8. NYHA functional class II or higher, judged by the investigator to be due to LVOT obstruction.
9. Has adequate acoustic windows, in the judgment of the investigator and the investigational site's echocardiography laboratory, to enable accurate TTEs.
10. Female subjects must not be pregnant or lactating and, if sexually active, must be using one of the following acceptable birth control methods from the Screening visit through 3 months after the last dose of investigational medicinal product (IMP). Hormonal contraceptives are not considered highly effective contraception for this study because MYK-461 could reduce the effectiveness of hormonal contraceptives.
 - Double-barrier method (e.g., vasectomy or male using a condom and female using a diaphragm or cervical cap)

- Barrier (e.g. male using a condom) plus non-hormonal intrauterine device (IUD) or intrauterine system (IUS)
 - Female is surgically sterile for 6 months or postmenopausal for 2 years. Permanent sterilization includes hysterectomy, bilateral oophorectomy, bilateral salpingectomy, and/or documented bilateral tubal occlusion at least 6 months prior to Screening. Females are considered postmenopausal if they have had amenorrhea for at least 2 years or more following cessation of all exogenous hormonal treatments and follicle-stimulating hormone (FSH) levels are in the postmenopausal range.
11. Male subjects with female partners (including postmenopausal partners) must agree to use highly effective contraceptive measures from the Screening visit through 3 months after the last dose of study medication. Highly effective contraception includes documented vasectomy, abstaining from sexual intercourse, double-barrier method (e.g., male using a condom and female using a diaphragm or cervical cap), or barrier plus hormonal contraception (e.g., male using a condom and female using hormonal contraception). As there may be a risk of drug being secreted in the ejaculate, male subjects (including men who have had vasectomies) whose partners are currently pregnant should use barrier methods for the duration of the study and for 3 months after the last dose of study medication. In addition, male subjects with sexual partners should use condoms for the duration of the study and for 3 months after the last dose of study medication, even if the partner is not pregnant or capable of becoming pregnant, in order to prevent passing MYK-461 to the partner in the ejaculate.
12. Must be able to complete the Dyspnea Numeric Rating Scale (NRS) and the KCCQ per established guidelines.

